#### **4.1.1 Screening Period**

At Screening, all elements of eligibility will be confirmed. A detailed description of study assessments to be performed at Screening is provided in the schedule of activities (Section 1.3).

#### **4.1.2 Sampling Period**

After the Screening Period, eligible study participants will enter a 7-day Sampling Period. Study participants can be admitted to the clinic either in the early morning of Day 1 or in the evening of the day before (Day -1) and may be discharged beginning on Day 3 after all planned assessments to be conducted at the clinic on Day 3 are completed (Section 1.3). Study participants, at their own discretion, may remain at the clinic and be discharged on a subsequent Study Day through Day 7 after completion of all planned assessments for that day's visit.

After discharge, visits may be completed in the study participant's home setting in the presence of a qualified nurse. To facilitate these visits, the study participant should have access to a telephone. Alternatively, study participants may visit the clinic for assessments and blood sampling, and/or to bring into the clinic the collected breast milk. Study participants who withdraw from the study during the Sampling Period will be asked to undergo the Early Withdrawal (EW) Visit procedures and will be encouraged to have a SFU telephone call on Day 57 ( $\pm 5$  days).

On Day 1, study participants will receive a single dose of rozanolixizumab based on their body weight (Table 4-1). Milk samples and blood samples will be collected to measure rozanolixizumab concentration throughout the Sampling Period and in accordance with the schedule of activities (Section 1.3). For each milk sampling interval, both breasts will be emptied by pumping, and any breast milk expressed will be stored and combined to provide the total volume of breast milk collected for that interval. A predose breast milk collection is taken on Day 1 (within 30 minutes predose) to ensure that both breasts are emptied prior to dosing. The time and date of the milk expression/sample collection must be recorded. Safety assessments will also be performed.

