**Figure 1-1: Study schematic**

D=Day; PK=pharmacokinetic(s)

a Study participants can be admitted to the clinic either in the early morning of D1 or the day before (Day -1) in the evening. Discharge can occur from D3 onward after all planned assessments to be conducted at the clinic on D3 are completed.

b The breast milk collection and sampling time points will be: within 30 minutes predose and 0 to ≤3, >3 to ≤6, >6 to ≤9, >9 to ≤12, >12 to ≤24, >24 to ≤36, >36 to ≤48, >48 to ≤60, >60 to ≤72, >72 to ≤84, >84 to ≤96, >96 to ≤108, >108 to ≤120, >120 to ≤132, and >132 to ≤144 (Day 7) hours after the start of infusion.

c Blood sampling: predose (within 60min before dosing) and 6h (±6min), 9h (±6min), 12h (±12min), 24h (±30min) (Day 2), 48h (±30min) (Day 3), 72h (±30min) (Day 4), 96h (±30min) (Day 5), and 144h (±24h) (Day 7) after the start of infusion.

---

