### 8.1 Breast milk sample collection

For each time breast milk is obtained, milk will be pumped from both breasts using an electronic breast pump and both breasts should be emptied. The milk from both breasts will be combined. If multiple expressions take place within a milk sampling interval, all breast milk collected will

be combined before a sample is taken. Total volume of breast milk expressed within a sampling interval will be recorded before a sample is taken.

Samples will be transferred by the study staff into transport tubes and stored at -20°C for shipment to the central laboratory. Participants with mastitis infection should not have samples collected until the infection is completely resolved.

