#### Estimated daily infant dosage from breastmilk

The estimated daily infant dosage of rozanolixizumab from breast milk will be calculated based on the concentration of rozanolixizumab in mature human breast milk for the PKs.

The amount of rozanolixizumab that the infant may consume following single rozanolixizumab dosing to the mother will be calculated as follows:

$$1. \text{ Estimated daily infant dosage (mg/kg/day)} = \text{M/P ratio} \times C_{\text{av,plasma}} \times 150\text{mL/kg/day}$$

Where M/P ratio is the milk:plasma ratio based on  $\text{AUC}_{(0-7\text{d})}$  and  $C_{\text{av,plasma}}$  is the average maternal plasma concentration calculated as  $\text{AUC}_{(0-7\text{d}),\text{plasma}}/7 \text{ days}$ .

This is based on the standardized mean milk consumption for a fully breastfed 2-month old infant of 150mL/kg/day.

$$2. \text{ Daily infant dosage (mg/day)} = \sum (\text{total drug concentration in each breast milk collection} \times \text{the expressed milk volume (ml) in each collection}) \text{ for each 24hour period of the 7 days postdose.}$$

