**Table 6–2: Pharmacokinetic Parameters and Estimation**

Parameter	Guideline for Derivation
$C_{max}$ , $t_{max}$	Obtained directly from the observed concentration-time data. Calculate for rozanolixizumab in breast milk and plasma
$Ae_{7d}$	Cumulative total amount excreted in milk to Day 7

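### Milk intervals after dosing need not end with an emptying, so the SAP's daily infant dosage in mg/day depends partly on when each woman pumps

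*Protocol*

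**What the plan says.** Protocol 4.1.2 (Sampling Period) sets the rule per interval: "For each milk sampling interval, both breasts will be emptied by pumping, and any breast milk expressed will be stored and combined". The only emptying given a time is the one before dosing: "A predose breast milk collection is taken on Day 1 (within 30 minutes predose) to ensure that both breasts are emptied prior to dosing".

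Protocol 8.1 adds a rule per expression: "For each time breast milk is obtained, milk will be pumped from both breasts using an electronic breast pump and both breasts should be emptied". It also covers pooling: "If multiple expressions take place within a milk sampling interval, all breast milk collected will" be combined before sampling, with the total volume recorded first.

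The postdose intervals (Figure 1-1 and the Table 1-1 footnotes) are four of 3 h up to 12 h and then eleven of 12 h, ending with ">120 to ≤132, and >132 to ≤144 (Day 7) hours after the start of infusion". That makes 15 intervals and six 24-hour periods.

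SAP 4.2.1.1, formula 2, defines the daily infant dosage in mg/day as concentration times expressed volume, summed over collections "for each 24hour period of the 7 days postdose". SAP 4.2.1.2 treats this as the total drug excreted in that 24-hour period. SAP Table 6-2 defines Ae7d as "Cumulative total amount excreted in milk to Day 7", and Fe is Ae7d divided by dose.

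**The concern.** Milk obtained at one emptying was secreted since the previous emptying. A collection therefore represents its interval only if the breasts are empty at both ends. The protocol recognises this at time zero, where the predose collection is there "to ensure that both breasts are emptied prior to dosing". It asks for the same at no later boundary.

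From 12 h onward, one expression anywhere in a 12-hour interval complies. A woman may pump just after 12 h and next at 36 h. The >24 to ≤36 h pool then holds almost 24 h of secretion, and the >12 to ≤24 h pool holds almost none of its own.

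At stake is the mg/day output, which SAP 4.2.1.1 lists under a secondary endpoint. Its first value starts from a fixed empty state and ends at an open one, so on average it is too low. Later values gain or lose milk at both ends, which adds scatter unrelated to drug transfer.

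**Working it through.** The documents give no figure on this point, so there is none to reproduce.

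**Inputs from the documents.** Emptying at time 0; the last interval of each 24-hour period is 12 h wide; last boundary 144 h; 12 to 15 women (Protocol 9.8); pumping 3 to 4 times a day, given only as an example for the 4 weeks before Day 1 (inclusion 6).

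**Assumptions, not from the documents.** Constant secretion of milk and drug, complete emptying at each expression, and timing independent between days.

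**Mass balance.** Let g_k be the hours from the last emptying in period k to the end of that period.
- First period: collected/true = (24 − g_1)/24.
- Later periods: collected/true = (24 + g_(k−1) − g_k)/24.
- Ae over 0 to 144 h: carry-over between periods cancels, leaving (144 − g_6)/144.

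**Limits of compliance** (g from 0 to 12 h). First period 12/24 to 24/24, or 50 to 100% of true. Later periods 12/24 to 36/24, or 50 to 150%. Ae at most 12/144 = 8.3% low.

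**Averages.** For g uniform on 0 to m, the mean is m/2 and the SD of a difference of two is √(2m²/12). For two random pumps in the last 12 h, the mean gap is 12/3 = 4 h and the SD of the difference is √(2 × 144/18) = 4 h.

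| Last emptying before the boundary | First 24 h, mean | Later days, SD | Ae7d and Fe, mean |
|---|---|---|---|
| Uniform, 0 to 6 h | 3/24 = 12.5% low | 2.45/24 = 10.2% | 3/144 = 2.1% low |
| Uniform, 0 to 8 h | 4/24 = 16.7% low | 3.27/24 = 13.6% | 4/144 = 2.8% low |
| Two random pumps per 12 h | 4/24 = 16.7% low | 4/24 = 16.7% | 4/144 = 2.8% low |
| One random pump per 12 h | 6/24 = 25% low | 4.90/24 = 20.4% | 6/144 = 4.2% low |

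The 6 to 8 h rows correspond to 3 to 4 spaced pumps a day. A simulation of the three uniform rows (4,000 draws each) agrees. It gives first-day means of 0.876, 0.832 and 0.750 and later-day CVs of about 10%, 14% and 20%. With the last pump within 6 to 8 h, the timing-only CV over all days runs from 8% (first day) to 14% (later days).

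**Sensitivity to a changing concentration.** Three one-compartment shapes were tried: tmax 24 h with half-life 24 h, and tmax 48 h with half-life 36 or 72 h. The first day then averages 74 to 83% of true with the last pump within 6 to 8 h, and 62 to 66% with one random pump. The worst compliant case is about 29 to 34%. Later-day means with the last pump within 6 to 8 h lie between 0.96 and 1.12, so they are no longer exactly unbiased. The maximum Ae loss falls to about 1 to 6%.

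**Quantities without volume.** The mg/kg/day dosage is M/P × Cav,plasma × 150 = (AUC_milk/AUC_plasma) × (AUC_plasma/7) × 150 = (AUC_milk/7) × 150 mL/kg/day. No expressed volume enters it, nor the relative infant dose built on it.

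**With closure at the boundary.** g = 0 gives 1.00 for every period and for Ae, under every profile tried. A 30-minute tolerance leaves at most 0.5/24 = 2.1% of a day and 0.5/144 = 0.3% of Ae.

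**The case against.** - **The main endpoints survive.** A reader might infer that the relative infant dose, or the primary milk concentration, is distorted. The documents do not support that: the algebra above contains no volume. Pump timing could reach the mg/kg/day dosage only through the time assigned to each pooled sample in the milk AUC. This stands and limits the point to the mg/day amount.
- **Ae7d is hardly touched.** A reader might also expect errors to accumulate over 15 intervals. They cancel, and only the last expression before 144 h matters. This stands.
- **Formula 2 uses expressed volume.** An infant drinks milk removed, not milk still in the breast, so on that reading nothing is biased. This stands in part, but SAP 4.2.1.2 equates the figure with the amount excreted in the period, which needs closed boundaries.
- **One random pump per 12 h is the bare minimum.** The figures for pumping within 6 to 8 h of the boundary are the fairer guide, though inclusion 6 does not bind women during sampling.
- **Everyone is in clinic on the first day.** Uneven timing at home cannot explain the first-day shortfall, which arises because the 24 h boundary is open. The clinic stay makes a closing pump easy but does not require one.
- **Times are recorded, and PK parameters use actual time.** A sum of concentration times volume contains no time, so this does not correct it, though it does make an adjustment possible.
- **The sponsor's collection instructions (Protocol 8.6) may set pump times.** They are not among the documents. Neither the protocol nor the SAP contains such a rule.

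**Conclusion.** The point holds for the daily infant dosage in mg/day. Under constant secretion and complete emptying, the first 24-hour amount averages about 12 to 17% low when the last pump falls within 6 to 8 h of the boundary. With one random pump per 12-hour interval it averages 25% low, and any compliant pattern gives 0 to 50% low. Later days carry a timing-only SD of about 10 to 14%, or 17 to 20% with randomly placed pumps.

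Scatter averages down over women: 13.6%/√12 = 3.9% on a daily mean. The first-day shortfall does not. A woman who pumps at the same clock times each day has little later-day error, so the scatter figures depend on timing varying between days.

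Ae7d and Fe are slightly low, by 2 to 4% on average and at most 8.3%. Collections need not match their intervals; for a woman who pumps at each interval's end they do. This is a modest, avoidable weakness in one defined output of a descriptive study, and it is cheap to remove.

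**What to change.** Add to Protocol 4.1.2 and 8.1: both breasts are fully emptied within 30 minutes before 24, 48, 72, 96, 120 and 144 h after the start of infusion, and preferably before the end of every interval; other expressions are allowed and pooled into their interval.

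In the SAP, flag 24-hour periods not closed on time. For those, add a supportive amount scaled by recorded times: amount × 24 / hours between the last emptying of the previous period and the last emptying of this one. This scaling assumes roughly constant secretion, so it supports the closing rule but does not replace it.

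The cost is fixed pumping times, some of them at home, with no added visits or assays. The 24, 48, 72 and 96 h boundaries coincide with blood draws (±30 min). The 144 h boundary does so only nominally, because that draw has a ±24 h window. At 120 h there is no draw, although Day 6 has a visit. If closing every interval is too burdensome, the six 24-hour boundaries are enough for the mg/day amount and Ae7d.

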#### **4.1.3 SFU**

A SFU assessment (via telephone with study staff) will be performed 8 weeks ( $\pm 5$  days) after dosing. Study participants who withdraw prematurely from the study will be encouraged to have a SFU telephone call 8 weeks ( $\pm 5$  days) after dosing.

### **4.2 Scientific rationale for study design**

The study is designed in accordance with the 2019 draft guidance from the US Food and Drug Administration (FDA): Clinical Lactation Studies: Considerations for Study Design (FDA, Guidance for Industry, 2019). Since this study is being undertaken in healthy study participants, only a single dose of rozanolixizumab is being investigated. Based on previous rozanolixizumab single-dose healthy volunteer studies, the majority of a single-dose plasma rozanolixizumab AUC is quantified by 7 days postdose. The breast milk Sampling Period encompasses 1 week (7 days) following the single rozanolixizumab dose to quantify total rozanolixizumab AUC in breast milk.

During this study, milk collection will occur at a minimum of 6 weeks postpartum to ensure mature milk is being produced, breast milk production is well established, and that this study is not an incentive for ceasing breastfeeding earlier than 6 weeks. An in-clinic stay of at least 48 hours will be used because the frequency of required plasma pharmacokinetic (PK) and breast milk sampling from predose to 48 hours postdose would be difficult to accomplish outside of the clinic and to enable the study participant to experience the breast milk sampling procedures prior to when the visits may be completed at the study participant's home.

Considering the uncertainty of how long rozanolixizumab could be present in the mammary glands (via binding to mammary tissue FcRn), breast milk feeding or resumption of breast milk feeding will not be allowed until 8 weeks after administration of rozanolixizumab, with the agreement that any breast milk collected (to maintain milk supply) during that 8-week period will be discarded. To remove the risk of exposing infants to rozanolixizumab, only lactating women who have voluntarily decided to cease or suspend breast milk feeding and who have established alternative sources of nutrition for their infant(s) will be eligible to participate in the study.

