#### Relative infant dose from breast milk

The relative infant dose of rozanolixizumab from breast milk will be calculated as follows:

$$\text{Estimated daily infant dosage (mg/kg/day)} / \text{maternal rozanolixizumab dosage (mg/kg/day)} \times 100$$

Where

maternal rozanolixizumab dosage (mg/kg/day)=Actual dose administered/(Day 1 weight\*7)

Plasma PK endpoints will be computed using actual blood sampling time points.

The following exploratory PK parameters will be derived for rozanolixizumab in breast milk:

- $C_{max}$ ,  $t_{max}$ ,  $AUC_{(0-7d)}$
- $Ae_{7d}$  (mg)=cumulative total amount excreted in milk to Day 7
- $Fe=Ae_{7d}/\text{administered dose (mg)} \times 100\%$
- Milk:plasma  $AUC_{(0-7d)}$  ratio

The following exploratory PK parameters will be derived for rozanolixizumab in plasma:

- $C_{max}$ ,  $t_{max}$ ,  $AUC_{(0-7d)}$

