**Table 6–2: Pharmacokinetic Parameters and Estimation**

Parameter	Guideline for Derivation
AUC (0-7d)	The AUC from zero time (pre-dose) to 144 h post dose will be calculated by a combination of the linear and logarithmic trapezoidal methods. Unless specifically requested and justified the linear up/log down trapezoidal method will be employed. Calculate for rozanolixizumab in breast milk and plasma.
Fe	$Ae_{7d}/\text{administered dose (mg)} \times 100 (\%)$
Milk:plasma AUC (0-7d) ratio	$AUC_{(0-7d)} \text{ in breast milk} / AUC_{(0-7d)} \text{ in maternal plasma} \times 100 (\%)$
Relative Infant Dose	$[(\text{Estimated}) \text{ Daily Infant Dosage (mg/kg/day)} / \text{Maternal Dosage (mg/kg/day)}] \times 100 (\%)$ (see Section 4.2.1.1 for details on the calculation of the estimated daily infant dosage)

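### Milk sampling to 144 h cannot be said to quantify total milk AUC, so RID and Fe are lower bounds on single-dose transfer if drug is still in milk at that time

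*Protocol*

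**What the plan says.** Protocol 4.2 states the purpose of the milk sampling window: "The breast milk Sampling Period encompasses 1 week (7 days) following the single rozanolixizumab dose to quantify total rozanolixizumab AUC in breast milk". The evidence offered, from earlier single-dose studies in healthy volunteers, is that "the majority of a single-dose plasma rozanolixizumab AUC is quantified by 7 days postdose". No percentage, half-life or milk profile is given, and Protocol 2.2 says that too little is known about excretion in human or animal milk. Later in 4.2, the reason for the 8-week restriction on breast milk feeding begins "Considering the uncertainty of how long rozanolixizumab could be present in the mammary glands".

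The last milk collection interval is ">132 to ≤144 (Day 7) hours after the start of infusion" (Protocol Figure 1-1, repeated in the schedule of activities). SAP Table 6-2 defines AUC(0-7d) as "The AUC from zero time (pre-dose) to 144 h post dose". Ae7d is the amount in milk to Day 7, and Fe divides it by the administered dose. In SAP 4.2.1.1, RID divides the estimated daily infant dosage by a maternal dosage built from the full dose given ("maternal rozanolixizumab dosage (mg/kg/day)=Actual dose administered", over Day 1 weight times 7). Neither document plans a milk sample after 144 h, an AUC(0-inf) or an extrapolated fraction.

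**The concern.** Within one section, the plan claims to measure all of the milk AUC, supports this with a statement about most of the plasma AUC, and says that persistence in the breast is unknown. These do not fit together. Milk need not follow plasma: if the gland retains drug and releases it slowly, the share of milk AUC seen by 144 h is smaller than the plasma share.

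This matters because Protocol 2.1 gives the infant dosage and relative infant dose as the information that breastfeeding women and their physicians need. RID carries no time window in its name. A reader will naturally take RID and Fe as transfer from one dose, whereas their numerators stop at 144 h and their denominators are complete.

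**Working it through.** **1. Length of the window.** From the listed intervals: 4 × 3 h + 11 × 12 h = 144 h = 6.0 elapsed days. Day 7 is correct as a calendar label with dosing on Day 1, but the postdose span is not 168 h.

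**2. What RID measures.** Inputs are from SAP 4.2.1.1, with M/P taken as a plain ratio:

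- M/P × C_av,plasma = (AUCmilk/AUCplasma) × (AUCplasma/7) = AUCmilk(0–144 h)/7
- Estimated daily infant dosage = 150 × AUCmilk(0–144 h)/7
- Maternal dosage = dose/(weight × 7)
- RID = 150 × weight × AUCmilk(0–144 h)/dose × 100%

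Numerical check with a placeholder AUC of 0.01 mg·day/mL, 70 kg and 560 mg: the infant dosage is 0.01/7 × 150 = 0.2143 mg/kg/day and the maternal dosage is 560/490 = 1.1429 mg/kg/day, giving 18.75%. The short form gives 150 × 70 × 0.01/560 × 100 = 18.75%.

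The 7s cancel. RID is therefore a cumulative ratio: milk exposure to 144 h against the whole dose. Changing the 7-day divisor in both places to 6 leaves it unchanged, so this point is separate from the 144 h versus 7-day mismatch. Fe has the same structure, with Ae7d over the whole dose.

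**3. Size under assumptions.** None of the following comes from the documents: first-order absorption with half-life 18 h, plasma half-life 24 to 72 h, and milk following plasma with a first-order lag of half-life 0 to 48 h. Share of total milk AUC captured by 144 h:

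| Plasma half-life | No lag | 24 h lag | 48 h lag |
|---|---|---|---|
| 24 h | 0.949 | 0.830 | 0.655 |
| 48 h | 0.802 | 0.655 | 0.503 |
| 72 h | 0.668 | 0.527 | 0.399 |

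The shortfall in RID against a total-AUC RID is 1 minus the entry: 1 − 0.949 = 5% to 1 − 0.399 = 60%. Fe loses about the same share if milk volume is steady. A second set of assumptions (milk tmax 1 to 3 days, milk half-life 1 to 14 days, in feasible combinations) gives 3% to 78%. The spread shows that the documents do not fix the size.

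**4. Daily infant dosage.** This is a rate. For an assumed profile with tmax 2 days and half-life 4 days (arbitrary units), AUC(0–168 h)/7 = 0.533 and AUC(0–14 d)/14 = 0.369. Averaging over a longer tail lowers the value. The mg/day amounts for each 24-hour period depend only on the day sampled.

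**5. Can the tail be recovered?** In the model of step 3 with a 48 h lag, milk tmax is about 101 h (plasma half-life 48 h) and 116 h (72 h). The last-interval concentration is about 91% and 97% of milk Cmax. Few or no points then lie on a terminal slope, so AUC(0-inf) would be unreliable where truncation is worst. The last concentration relative to Cmax can still be calculated and is informative there.

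**The case against.** Four arguments have weight.

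- **The endpoints are openly windowed.** AUC(0-7d), Ae7d to Day 7 and a 7-day Sampling Period are stated, and SAP 4.2.1.1 says that M/P rests on AUC(0-7d). Only the rationale in 4.2 claims the total, and that sentence drives no calculation. This stands, but RID and Fe carry no window in their names.
- **An unfinished profile would be visible.** A reader might infer that the plan would hide truncation. It would not: SAP 4.2.1.2 plans concentration listings and summaries at each nominal time, individual and mean profiles with the LLOQ on the semi-logarithmic plots, and the amount excreted in each interval. What is missing is a figure for the missing share, or any link from it to RID and Fe.
- **Direction and size are not established.** A reader might infer that RID and Fe are known to be biased low. The documents do not support that. Protocol 4.2 speaks of persistence in the gland, not of measured persistence in milk, and the half-lives and lags above are assumed.
- **A fixed window is a legitimate choice** in a descriptive study without hypotheses. It is; the objection is to the claim made for it.

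A reader might also infer that the infant dosage is understated by the missing tail. Step 4 shows that a tail does not by itself make a daily rate after a single dose too low. It would matter only if the figure were read as exposure under repeated weekly dosing.

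**Conclusion.** The concern holds in a limited form. The statement in Protocol 4.2 that the window quantifies total milk AUC has no support in the documents and conflicts with the uncertainty stated in the same section. RID and Fe relate milk data to 144 h to the whole dose, so they are lower bounds on single-dose transfer if drug is still in milk at 144 h. If milk has fallen below quantification by then, the loss may be negligible. The algebra is exact and needs no assumption. The size, about 5% to 60%, rests entirely on the assumed absorption, half-lives and lags and cannot be narrowed from the documents. The daily infant dosage is outside this conclusion.

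**What to change.** 1. In Protocol 4.2, change the claim of total rozanolixizumab AUC in breast milk to *AUC in breast milk through 144 h*.
2. In SAP 4.2.1.1 and Table 6-2, add from samples already planned: the last-interval milk concentration as a percentage of milk Cmax for every participant; and, only where a terminal slope is reliably estimable, the percentage of milk AUC(0-inf) that is extrapolated, with a supportive RID = 150 × weight × AUCmilk(0-inf)/dose × 100%. State in advance what counts as reliably estimable, and report how many participants were not estimable.
3. Label RID and Fe *through 144 h* in all tables. Where the last milk sample is quantifiable, describe them as lower bounds and show the last-concentration/Cmax figure beside them. A value above the LLOQ alone does not separate a small tail from a large one.

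The cost is one protocol sentence, a few derived rows and table labels. No samples, visits or procedures are added. The downside is that AUC(0-inf) will be missing for participants with slow milk decline, and the RID statement may become less favourable. If milk has cleared, the added rows will show it.
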